Clinical investigation plan

C24-748 (EX-MKTG-160)

**A multisite investigation of the wearing compliance of
spectacles for myopia control**

**A clinical evaluation for
CooperVision Inc.**

[figure not shown]
Principal Investigator
[name]

April 2024

Contents

| | |
|--|-----------|
| Document control | 3 |
| Study summary | |
| Section 1. Overview | 5 |
| 1.1 Background | 5 |
| 1.2 Personnel | 5 |
| 1.3 Study objectives | 5 |
| 1.4 Study design | 5 |
| 1.5 Statistical considerations | 5 |
| 1.6 Risk analysis | 6 |
| 1.7 Clinical trial registration | 7 |
| Section 2. Resources | 8 |
| 2.1 Subject selection | 8 |
| 2.2 Subject discontinuation | 8 |
| 2.3 Safety parameters, adverse events and concurrent illnesses | 9 |
| 2.4 Study termination | 9 |
| 2.5 Protocol deviations | 9 |
| 2.6 Study control | 10 |
| 2.7 Documentation | 10 |
| 2.8 Data collection and analysis | 10 |
| 2.9 Study completion | 10 |
| 2.10 Subject confidentiality | 10 |
| 2.11 Study monitoring | 10 |
| Section 3. Subject management | 12 |
| 3.1 Visit scheduling | 12 |
| 3.2 Visit conduct | 12 |
| 3.3 Monitoring subject compliance | 13 |
| Section 4. Study co-ordination | 14 |
| 4.1 Document processing | 14 |
| 4.2 Disclosure | 14 |
| 4.3 Personnel | 14 |

Document control

Study summary

This multi-centre study will compare the wearing patterns of spectacles prescribed for myopia control at about four optometry practices. Up to 60 established (use of ≥ 3 months) juvenile wearers will be recruited and their wearing patterns over one week of a month's wear will be evaluated. A study summary is shown in Table 1.

| Visit | Procedures |
|---------|---|
| | |
| Visit 1 | Subject attends their own optometry practice Questions about the study answered Consent form and assent forms signed Temperature sensor fitted to frame (or side with sensor fitted) |
| Visit 2 | Subject attends optometry practice Subject discharged from study |

Table 1: Study summary.

Section 1. Overview

1.1 Background

This study seeks to compare the wearing patterns of spectacles prescribed for myopia control. [REDACTED]

[REDACTED]

[REDACTED]

[REDACTED]

[REDACTED]

[REDACTED]

1.3 Study objectives

This study aims to compare the wearing patterns of spectacles for myopia control across different ages, different levels of myopia and between males and females.

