1.5 Statistical considerations

The principal hypothesis to be tested in this work is that wearing times for young and old wearers will be the same. Wearing time data are likely to be normally distributed and so the impact of age will be explored using linear regression models or other parametric methods.

Deviations from this plan will be discussed in the final report. Deviations may be necessary due to differences between the actual data distribution compared with the anticipated data distribution.

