1.5.2 Power analysis

Power analysis was conducted based on information from a previous study [REDACTED]

[REDACTED], assuming (a) that males vs. females are compared and (b) younger vs. older subjects are compared. For sex, power analysis based on previous data in spectacle wearers shows that for a two-sided two-sample t-test with an alpha of 0.05, assuming standard deviations of 0.95 for females and 2.61 for males, a sample size of 17 subjects in each group is required to detect a 2-hour difference in daily wearing time between groups with 80% power.

For age, power analysis on the same basis, assuming standard deviations of 3.31 for older subjects (> 10 years) and 0.68 for younger subjects (< 10 years), a sample size of 25 subjects in each group is required to detect a 2-hour difference in daily wearing time between groups with 80% power.

Given this, 60 subjects will be recruited to comprise approximately 50% males and 50% females, and with subjects recruited across the full age range. Subjects will be recruited into the following prescription range 'bins' (mean sphere) in approximately equal numbers; 1) plano to -1.50DS, 2) -1.75 to -3.75DS and 3) -4.00DS and above.

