2.1 Subject selection

In this work, up to 60 subjects will be recruited – approximately 15 at each of about four UK optometry practices. Note that the subjects will be recruited to comprise approximately 50% males and 50% females, and with subjects recruited across the age range 6-15 years. Subjects will be recruited into the following prescription range 'bins' (mean sphere) in approximately equal numbers; 1) plano to -1.50DS, 2) -1.75 to -3.75DS and 3) -4.00DS and above.

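### The principal age test is not tied to a method that allows for unequal variance, although the plan anticipates SDs of 3.31 h and 0.68 h; level of myopia has no named analysis

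*Combined protocol and SAP*

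**What the plan says.** Section 1.3 sets three comparisons: the study is to "compare the wearing patterns of spectacles for myopia control across different ages, different levels of myopia and between males and females".

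Section 1.5 singles out one of them: "The principal hypothesis to be tested in this work is that wearing times for young and old wearers will be the same". It expects normally distributed wearing times and on that basis says "the impact of age will be explored using linear regression models or other parametric methods". It does not say whether age enters as two groups or as a continuous variable, or which standard error is used. Departures from the plan are allowed for "differences between the actual data distribution compared with the anticipated data distribution".

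Section 1.5.2 sizes the study "assuming (a) that males vs. females are compared and (b) younger vs. older subjects are compared", using a two-sided two-sample t-test at 0.05. For age it gives 25 per group, "assuming standard deviations of 3.31 for older subjects (> 10 years) and 0.68 for younger subjects (< 10 years"; for sex it gives 17 per group with SDs of 0.95 and 2.61. Both target a 2-hour difference with 80% power.

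Recruitment is to be about half male and half female, "and with subjects recruited across the full age range". Prescription is filled "in approximately equal numbers; 1) plano to -1.50DS, 2) -1.75 to -3.75DS and 3) -4.00DS and above" (Section 2.1). No numbers are set by age group.

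**The concern.** The standard errors that regression software reports by default assume one common residual variance. On the plan's own figures the older group's SD is almost five times the younger group's. With such a gap, the equal-variance error is right only when the two age groups are about the same size. If the more variable group is the smaller one, the error is too small and false positives rise. If it is the larger one, the error is too large and power is lost. Section 1.5 argues from normality, which does not bear on this. Its deviation clause does not help either, because the inequality is anticipated and so is not a departure from expectation.

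At stake is whether the principal test holds its 5% level whatever age mix is recruited, and whether its method is settled before the data are seen. The same openness affects level of myopia, which is a stated objective but appears elsewhere only as recruitment bins.

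**Working it through.** **Inputs.** From Section 1.5.2: age SDs 3.31 (older) and 0.68 (younger); sex SDs 0.95 and 2.61; difference 2 h; two-sided 0.05; 80% power; 25 and 17 per group; total 60. From Section 2.1.3: ages 6 to 15. Assumed: normal data, a full 60 subjects, and the splits and SD shapes named below.

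**1. The plan's sample sizes.** Welch test: SE = √(s₁²/n + s₂²/n); df = (v₁+v₂)² / [(v₁²+v₂²)/(n−1)] with vᵢ = sᵢ²/n; power from the noncentral t with noncentrality 2/SE.

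- Age, n = 25: SE = √[(10.956 + 0.462)/25] = 0.676; noncentrality 2.96; df 26.0; power 81.3%.
- Sex, n = 17: SE = √[(0.903 + 6.812)/17] = 0.674; noncentrality 2.97; df 20.2; power 80.7%.

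These are the smallest n that reach 80%, so both stated figures reproduce. With pooled degrees of freedom the answers are 24 and 17; with the normal approximation, 23 and 16. Only the unequal-variance calculation gives both 25 and 17.

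**2. Size of the inequality.** Age: (3.31/0.68)² = 4.87² = 23.7. Sex: (2.61/0.95)² = 7.5.

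**3. Default error against true error, grouped age.** Default SE² = [((nₒ−1)·3.31² + (n_y−1)·0.68²)/(nₒ+n_y−2)]·(1/nₒ + 1/n_y). True SE² = 3.31²/nₒ + 0.68²/n_y.

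- 24 younger, 36 older: default √[6.795 × 0.0694] = 0.687; true √0.3236 = 0.569; ratio 1.21 (too wide).
- 35 younger, 25 older: default 0.574; true 0.672; ratio 0.85 (too narrow).
- 40 younger, 20 older: default 0.541; true 0.748; ratio 0.72.
- 30/30: ratio 1.00.

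Simulated rejection rates (1,000,000 runs per split):

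| Younger/older | Type I, default | Type I, Welch | Power for 2 h, default | Power, Welch |
|---|---|---|---|---|
| 30/30 | 5.4% | 5.0% | 88.9% | 88.2% |
| 24/36 | 2.1% | 5.0% | 85.8% | 92.9% |
| 20/40 | 0.9% | 5.0% | 81.3% | 94.9% |
| 35/25 | 9.9% | 5.0% | 89.4% | 81.7% |
| 40/20 | 16.1% | 5.0% | 88.8% | 72.0% |

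HC3 (heteroscedasticity-consistent) errors in the two-group regression give 4.9% to 5.4% over these splits.

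**4. Which split is plausible.** Ages 6 to 15 are ten year-groups. Spread evenly, 60 subjects give 6 per year: 4 × 6 = 24 under 10, 6 aged 10, and 5 × 6 = 30 over 10. As written, the two groups leave out children aged exactly 10. Counting them as older gives 24/36. Even recruitment is an assumption, because the plan asks only for a spread over the range.

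**5. Continuous age, even spread (6 per year), no age effect.** How the SD changes with age is not given, so three shapes were tried:

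| Assumed SD shape | Type I, default | Type I, HC3 |
|---|---|---|
| Steps from 0.68 to 3.31 at age 10 | 3.5% | 5.4% |
| Rises linearly | about 6% to 8%, by where the line is anchored | about 5.5% |
| Rises exponentially | about 13% | about 5.8% |

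**6. Sex and myopia.** With equal groups the default and Welch standard errors are algebraically identical, as in the 30/30 age case, so the half-and-half target largely protects the sex comparison. For the three prescription bins there is no test, model, SD or power to check.

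**The case against.** The strongest reply is that the plan nowhere specifies equal-variance errors. Welch's test is itself a parametric method, so the wording of Section 1.5 permits it, and the sample sizes suggest that the planners had unequal variances in mind. That is correct, and a reader who inferred that the plan prescribes the wrong standard error would go beyond the text. What stands is narrower: permission is not commitment, and the method named first carries an equal-variance error by default.

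A second reply is that the 10% and 16% error rates need a younger majority, which nothing in the documents predicts. Even recruitment over 6 to 15 leans older, where a default test is conservative and still has more than the planned 80% power. This also stands for grouped age, so inflation should not be presented as the expected outcome. It does not carry over to continuous age, where an even spread can inflate the error if the SD rises steadily with age.

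Third, sex is not wholly without an analysis: Section 1.5.2 gives a test, alpha, SDs and effect size for it. They are given as a sizing basis rather than a planned analysis, but sex should not be put on the same footing as level of myopia.

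Finally, one might infer that the age effect is confounded by level of myopia. The visible documents give neither their correlation nor any effect of myopia on wear. That is an open possibility, not a demonstrated bias.

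**Conclusion.** The point holds in limited form. Section 1.5 does not commit the principal age test to a method that allows for the variance ratio of about 24 that Section 1.5.2 anticipates, while the sample sizes fit exactly such a method.

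If default errors were used on grouped age, the type I error would run from about 1% (20/40 younger/older) to 16% (40/20), with nothing in the plan fixing the split. The likelier consequence is lost power: about 7 points at 24/36 (85.8% against 92.9%). For continuous age with an even spread, the type I error could lie anywhere from about 3.5% to 13%, depending on an SD shape that the documents do not give. All of this rests on the plan's SDs being right, normal data and 60 analysed subjects.

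That level of myopia has no named analysis is a plain gap against Section 1.3, but by itself it is mainly missing detail. The plan should be corrected; the study is not undermined, since a sound analysis is already within what the text allows.

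**What to change.** In Section 1.5:

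1. State one form of age in advance. If it is the two groups of Section 1.5.2, say which group takes children aged exactly 10, and test with Welch (or regression with HC3 errors). If age is continuous, use linear regression with HC3 errors.
2. In the same sentence name the secondary comparisons: sex by Welch, and the three prescription bins as estimated differences with 95% confidence intervals, both labelled secondary.
3. Optionally, add one supportive regression containing age, sex and prescription bin with HC3 errors. The unadjusted age comparison stays the principal test.

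The change is wording only, since age, sex and prescription are already needed for recruitment. At 30/30 the power cost is 88.9 − 88.2 = 0.7 points, and at 24/36 power rises. With a younger majority the honest power is lower (82% at 35/25, 72% at 40/20); the higher figures under default errors come from an inflated error rate. With continuous age skewed young, HC3 can still run slightly high, at about 6% to 7%. The optional model gives a less precise age estimate: its SD rises 2% to 4% if age and prescription are unrelated and 12% to 26% at an assumed correlation of 0.6.

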1.4 Study design

This will be an unmasked multi-centre study which is controlled by cross-comparison. The wearing patterns of up to 60 established spectacle wearers will be evaluated via the use of temperature sensors fitted to the side of their spectacles. [REDACTED]

[REDACTED]

[REDACTED]. Subjects will wear the sensor for approximately one month. The data from the final week of this period will be used for analysis, in an attempt to minimise 'unusual' wear patterns which may occur early in the study as the subject adapts to being on a clinical study.

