2.1.3 Inclusion criteria

Subjects will only be eligible for the study if:

1. They are aged between six and 15 years old.
2. Their parent or guardian understands the rights of the subject and are willing to sign a statement of informed consent.
3. They understand the study at a level appropriate for their age and are willing to sign a statement of assent.
4. They and their parents or guardians are willing and able to follow the protocol.
5. They currently use spectacle lenses for myopia control and have done so for at least three months.
6. They agree not to participate in other clinical research for the duration of this study.

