2.5.1.1 Use of spectacles

Spectacles should be worn in line with normal wear patterns for the subject.

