3.1 Visit scheduling

Subjects will be required to attend an online information meeting followed by two clinic visits – an initial visit (Visit 1) and a follow-up visit (Visit 2), after approximately one month. Acceptable date ranges are shown in Table 2.

| Visit | Target | Allowable range |
|-------|----------------------|----------------------------|
| 1 | N/A | N/A |
| 2 | 28 days from Visit 1 | 20 to 40 days from Visit 1 |

Table 2: Visits and allowable ranges.

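### In the visible text the one analysed week is not controlled, explicitly recorded or adjusted for by school term or holiday, so an uneven share of holiday weeks would bias the age, sex and myopia comparisons

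*Combined protocol and SAP*

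**What the plan says.** Section 1.4 has children wear the sensor for about a month and analyses only its last week: "The data from the final week of this period will be used for analysis, in an attempt to minimise 'unusual' wear patterns". The unusual patterns it has in mind are those "which may occur early in the study as the subject adapts to being on a clinical study". No other source of an untypical week is mentioned.

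The timing of that week follows from Visit 2, which section 3.1 targets at 28 days and allows at "20 to 40 days from Visit 1". Section 2.5.1.1 adds: "Spectacles should be worn in line with normal wear patterns for the subject".

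The subjects are schoolchildren. Section 2.1.3 requires that "They are aged between six and 15 years old", and section 2.1 recruits "approximately 15 at each of about four UK optometry practices". Section 1.3 compares wear "across different ages, different levels of myopia and between males and females", and section 1.5 makes young against old the principal hypothesis, with age examined by linear regression or a similar parametric approach.

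The visible text is silent on four things:
- **Scheduling:** no mention of term, holiday, season or a common recruitment period.
- **Recording:** the Visit 2 list in 3.2.4 covers removal of the sensor, payment and discharge. Concurrent illness (section 2.3) is the only named circumstance of the week that goes on the CRF.
- **Analysis:** sections 1.5 and 1.5.1 name no calendar covariate, restriction or sensitivity analysis.
- **Balance:** sections 1.5.2 and 2.1 balance sex and prescription bin and spread age, but do not balance fitting dates.

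Parts of sections 1.4 and 2.1.2, and the content of 3.2.1, are redacted. These statements cover the legible text only.

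**The concern.** Section 1.4 accepts that an untypical week can distort the outcome, then guards against one cause of it. A child's day is arranged differently in term and in holiday, so wearing time may differ too, perhaps by a different amount at different ages.

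With one week per child, term against holiday is a difference between children, and nothing within a child averages it out. If the older group happens to supply more holiday weeks than the younger group, the calendar difference becomes part of the estimated age difference. The same holds for sex and for prescription bin. If shares are equal and the calendar effect is the same in each group, the only cost is extra spread.

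**Working it through.** **1. Where the analysed week can fall.** Count Visit 1 as day 0 and let the final week end on the day of Visit 2. The week is then:
- days 14-20 for a Visit 2 on day 20 (20 - 6 = 14);
- days 22-28 at the target (28 - 6 = 22);
- days 34-40 for a Visit 2 on day 40 (40 - 6 = 34).

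Two children fitted on the same day can be analysed on weeks up to 20 days apart, before staggered recruitment is added.

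**2. The plan's own sample sizes (section 1.5.2).** Two-sided alpha 0.05, difference 2 h, unequal-variance (Welch) t-test with noncentrality 2 / sqrt(s1²/n + s2²/n):
- Sex, SDs 0.95 and 2.61: 17 per group, power 0.807. The plan states 17.
- Age, SDs 3.31 and 0.68: 25 per group, power 0.813. The plan states 25.
- Age at 30 per group (60 split evenly, an assumption): power 0.88.

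**3. Formulas for a calendar effect.** Let h be the holiday-minus-term difference in h/day and p the share of a group whose analysed week is holiday. The documents give neither, so both are assumed.
- Added within-group variance: p(1 - p)h²
- Shift in the group difference: (pA - pB) × h

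**4. Balanced shares, age comparison.** For p = 0.25 and h = 2, the added variance is 0.25 × 0.75 × 4 = 0.75. The SDs become sqrt(3.31² + 0.75) = 3.42 and sqrt(0.68² + 0.75) = 1.10.

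| h (h/day) | n per group for 80%, p = 0.25 to 0.5 | Power at 30 per group |
|---|---|---|
| 1 | 25-26 | 0.87 |
| 2 | 27-28 | 0.83-0.84 |
| 3 | 31-33 | 0.76-0.79 |

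Up to 2 h/day, 60 subjects still reach 80%. Only at 3 h/day do they fall short.

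**5. Chance imbalance.** With 30 per group and p = 0.25, the SD of the difference in shares is sqrt(2 × 0.25 × 0.75 / 30) = 0.11. A one-SD imbalance shifts the observed difference by 0.11 × 1 = 0.11 h to 0.11 × 2 = 0.22 h. This shift is conditional on the imbalance that occurs. Over repeated studies it averages to zero and is the extra variance of step 4.

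**6. Systematic imbalance.** A gap of 25 points gives 0.25 × 1 = 0.25 h to 0.25 × 2 = 0.5 h, or 12.5% to 25% of the 2 h target. With no true age difference, 30 per group and holiday shares of 50% (older) and 25% (younger), the type I error is 0.07 at h = 1 and 0.11 at h = 2, instead of 0.05.

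**The case against.** The strongest reply is that nothing in the documents shows that wear differs between term and holiday, or that the groups would differ in their holiday share. Every practice draws on its own patients across the age range. A 25-point gap lies 0.25 / 0.11, or about 2.2, chance SDs from balance, so it needs a systematic cause and none is documented. The planning SDs come from earlier spectacle wearers whose calendar mix is not visible, so they may already contain some of this variance. All of this stands, and it limits the size that can be claimed. It does not close the gap, because no visible provision prevents or handles an imbalance.

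Four stronger readings are tempting, and the documents do not support them:
- **That the problem could not be repaired later.** Checking the visit window requires visit dates, and each child's practice is known, so the week could probably be classed afterwards. Dates alone would not show a particular school's calendar or family travel, and an adjustment chosen after seeing the data is weaker than one set in advance.
- **That a child fitted at the end of term is necessarily analysed in holiday.** A holiday of two weeks or less that starts at Visit 1 covers at most days 0-13 and is over before the earliest analysed week, days 14-20. The risk is from a longer holiday, or from one that starts about three weeks after fitting.
- **That the imbalance could readily reach 40 points.** That is about 3.6 chance SDs (0.40 / 0.11), with no documented mechanism.
- **That analysis should be confined to term weeks.** Holidays are part of the normal wear described in section 2.5.1.1, and section 2.1.1 favours including all subject data. At a 25% holiday share, dropping those children leaves 0.75 × 30, or about 22 per group, below the plan's 25.

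**Conclusion.** The point holds as a gap in the visible plan. One week per child is analysed, and its place in the school calendar is not controlled, explicitly recorded or adjusted for. An uneven holiday share between groups would bias the age, sex and myopia comparisons.

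The likely size is modest. At an assumed 1-2 h/day difference, a one-SD chance imbalance moves the age comparison by roughly 0.1-0.2 h. A systematic 25-point imbalance would move it by 0.25-0.5 h against the 2 h target. If shares are balanced, the planned 60 still gives at least 80% power.

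These figures rest on the assumed term-holiday difference, a 25% holiday share for the chance calculation, an even split of 30 per group, and the two-group comparison of section 1.5.2 standing in for the regression. A timing rule in the redacted text could change the conclusion. The change is worth making because it is cheap, not because a large bias has been shown.

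**What to change.** - **Section 3.2.4:** add one Visit 2 CRF line classing each of the seven analysed days as school day, weekend, or school holiday/travel, with a stated rule for weekend days inside a holiday. The questioning of child and parent already planned in section 3.3 is an occasion to ask.
- **Section 1.5:** prespecify a term/holiday covariate, the number of holiday days in the analysed week, in the linear regression. Keep all subjects. Add a sensitivity analysis restricted to term weeks. The single covariate assumes the same holiday effect at every age, and the sensitivity analysis is a check on that.
- **Section 3.1 (optional):** use the existing visit window to place the analysed week in term where that is convenient, without making it mandatory.

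**Cost:** one CRF line and one model degree of freedom. No extra visit or subject is needed. The term-week analysis will have fewer children and so less power, which is why it should not be primary.
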